#### 4.0 Statistical Design:

**Power considerations.** As an exploratory study designed to help us understand feasibility and potential efficacy, this trial is not meant to be adequately powered for testing hypothesized effects. Rather it will help us understand the potential efficacy for weight loss and our benchmarks for feasibility (retention, adherence, satisfaction) and other secondary outcomes.

**Data analytic plan.** As we have no control group, we will simply examine means and standard deviations of changes and whether we have reached our benchmarks for the trial. See below for details.

#### Intervention outcomes at 4 months

Intervention feasibility and acceptability	
Outcome	Measure/Method
Recruitment and retention	We will report numbers for recruitment and retention using a CONSORT diagram. Number and reasons for failure to complete follow-up assessments will be reported.
Intervention acceptability and satisfaction	At completion, participants will report the following: 1) satisfaction with each intervention component; 2) satisfaction with the intervention overall; 3) likelihood of referring the intervention to a friend; 4) intervention aspects perceived to be most useful; and 5) suggestions for improvement the intervention.
Intervention engagement	Frequency of lesson log-ins and adherence to the recommended diet based on dietary recall. In our previous study in adults with type 2 diabetes, by 4 months participants had logged into more than 95% of lessons.
Open-ended questions	We will ask participants open-ended questions about various aspects of their experience to explore, in an open-ended way, their opinion about the intervention and trial.
Preliminary efficacy	
Primary outcome	Body weight, as measured by a scale we will mail participant (which connects using its own cellular network to our study databases). We will examine the average percent weight loss as well as the percentage of participants in each group who lose a clinically significant amount of weight, at least 5%, which is thought to lead to metabolic improvements and reductions in the future risk of type 2 diabetes [10].
Exploratory metabolic and cardiovascular health outcomes	To reduce the future risk of type 2 diabetes, our goal is to improve glycemic control (glycated hemoglobin; HbA1c), insulin resistance (homeostatic model assessment from fasting blood glucose and insulin; HOMA), lipids (triglycerides and cholesterol), free testosterone [37], and inflammation (C-reactive protein) [38, 39]. These measurements will all occur at MLabs, a local laboratory run by Michigan Medicine.

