
*Exclusion criteria:* a non-English speaker; inability to complete baseline measurements; a substance abuse, mental health, or medical condition that would interfere with participation (such as current chemotherapy); pregnant or planning to get pregnant in the next 6 months; type 1 or type 2 diabetes; baseline aspartate aminotransferase (AST) or alanine aminotransferase (ALT)  $> 2$  times normal; baseline renal disease defined as BUN  $> 30$  mg/dL or serum creatinine  $> 1.4$  mg/dL; baseline uncorrected thyroid disease (TSH  $< 0.45$  mIU/ML or  $> 4.5$  mIU/ML); breastfeeding or less than 6 months post-partum; planned or history of weight loss surgery; vegan or vegetarian; currently enrolled in a weight loss program or other investigative study that might conflict with this research; taking medications known to cause weight gain or loss; taking hypoglycemic medications other than metformin or medications known to affect metabolism; or patients with other etiologies of anovulation and hyperandrogenism, e.g., Cushing's disease, thyroid dysfunction, elevated prolactin levels, signs of congenital adrenal hyperplasia, organic intra cranial lesion such as a pituitary tumor, or suspected adrenal or ovarian tumor secreting androgens.

After passing preliminary eligibility based on an online screening survey (using an online consent form), we will ask participants to (1) have their primary physician approve their participation in the trial, (2) answer online surveys about self-reported physical and psychological well-being, (3) go to one of more than 20 local locations to get their blood measured, (4) perform a 3-day food diary, and (5) weigh themselves on the bodyweight scale that we will mail them.

[figure not shown]

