**Core Intervention:**

**a) Dietary self-monitoring using a free application.** We will ask participants to track their diet using a free online and mobile application, MyFitnessPal (which our participants have found easy to use, has a wide variety of foods in its database, and has over 150 million users). If by the time we begin the trial there is an easier-to-use diet-tracking program more tailored to the very low-carbohydrate diet, we will consider using that program instead.

**b) Body weight self-monitoring using a digital scale.** We will ask participants to track their body weight with an easy-to-use remote scale provided by the study. The scale connects via its own cellular network and therefore does not require any Wi-Fi passwords or setup by participants, simplifying ease of use. We will use this information to monitor participant success and tailor coaching support.

**c) Goals for physical activity and sleep.** We will describe the health benefits of physical activity [25]. Using the Diabetes Prevention Program [26] as a guide, participants will be encouraged to engage in moderately intense physical activity for at least 150 minutes a week. The intervention will also describe the connection between lack of sleep and weight gain [27], impaired insulin signaling [28], and type 2 diabetes [29]. Participants will be encouraged to practice sleep hygiene and aim for 7-9 hours a night of sleep.

**d) Training in positive affect and mindfulness (extra psychological supports).** We will teach these skills, how they are expected to help, research supporting them, and suggestions for practicing them.

**e) Text messages.** Reminders about targeted behaviors are tied to greater behavioral adherence [30, 31]. Thus, to deliver convenient reminders, as [name] has done in her previous research, we will send automatic, motivational, and educational skill-relevant messages about 5 times a week to participants [32, 33].

**f) Mailed materials.** To attempt to help participants change their diet and increase their self-efficacy for new foods, at baseline participants will receive an assortment of difficult-to-find foods that are allowed on their diet (such as coconut and almond flour) and at baseline and 1 and 3 months later we will mail them lay-press cookbooks. Possible materials are pictured to the right.

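### The primary weight summary, as written, leaves out women with no month-4 weight, although earlier readings from the study scale could be used to estimate the result for all enrolled women (minor)

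*Combined protocol and SAP*

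**What the plan says.** Section 4.0 (Data analytic plan) notes that there is no control group and gives the whole analysis in one line: "we will simply examine means and standard deviations of changes", plus a check against benchmarks. It then points to the outcomes table.

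The Primary outcome row of that table (Intervention outcomes at 4 months) reads: "We will examine the average percent weight loss as well as the percentage of participants in each group who lose a clinically significant amount", set at 5% or more. The row defines weight by the mailed scale, "which connects using its own cellular network to our study databases".

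On missing follow-up, the Recruitment and retention row says: "Number and reasons for failure to complete follow-up assessments will be reported". The readable text gives no analysis set, imputation, model or sensitivity analysis for missing weights.

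Section 3.0 asks women at baseline to "weigh themselves on the bodyweight scale that we will mail them", and repeats that step at month 4. It gives no day range and no rule for choosing among several readings. Between those two points, Core Intervention item b says: "We will ask participants to track their body weight with an easy-to-use remote scale provided by the study". The use stated there is: "We will use this information to monitor participant success and tailor coaching support". How often women should weigh themselves is not stated.

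**The concern.** A change score needs a month-4 weight. With raw means of change as the only method, a woman without one contributes nothing to the primary mean, whatever her earlier readings showed. For the 5% rate, the wording about each group does not settle the denominator in a single-arm study: all enrolled women and weighed women both fit.

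If the women who stop differ in weight loss from those who continue, the weighed-only figures describe a selected group. Weight is the primary efficacy outcome, and section 1.0 says the study's results will help the team finalise the intervention and propose a larger randomized trial. The study also receives data that could reduce the problem: a woman who misses month 4 may have transmitted weights for weeks or months beforehand.

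**Working it through.** **Is there a plan figure to reproduce?** No. The documents give the sample size (30, section 1.0) but no expected retention, mean loss, SD or dropout mechanism. Everything below except the 30 is an assumption chosen to show size.

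**Step 1. The mean, by arithmetic.** With m of 30 missing, a weighed-only mean loss of 6.0% and a mean loss x in the missing women:

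all-enrolled mean = ((30 − m) × 6.0 + m × x) / 30

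For m = 6 and x = 0, 4, 6, 8, this is (144 + 6x)/30 = 4.8, 5.6, 6.0 and 6.4%. The weighed-only figure is too high, right or too low depending on x, which the documents do not give.

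**Step 2. The 5% rate, by counting.** With r responders among weighed women:

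| Missing m | r | Weighed only, r/(30 − m) | Missing as non-response, r/30 | Missing as response, (r + m)/30 |
|---|---|---|---|---|
| 3 | 16 | 59.3% | 53.3% | 63.3% |
| 6 | 14 | 58.3% | 46.7% | 66.7% |
| 9 | 13 | 61.9% | 43.3% | 73.3% |

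The bounds are m/30 wide: 10, 20 and 30 points. They show how far the choice of rule can move the reported figure. They do not measure bias.

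**Step 3. Plausible bias, by simulation.** There are four monthly windows. Monthly loss is 1.2 points plus a personal drift (SD 0.8) and a monthly shock (SD 1.3), with measurement SD 0.5.

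- True month-4 mean: 4 × 1.2 = 4.8%.
- SD: √((4 × 0.8)² + 4 × 1.3² + 0.5²) = √17.25 = 4.15.
- SE at n = 30: 4.15/√30 = 0.76.
- True 5% rate: 48%.

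Dropout before windows 2, 3 and 4 is logistic in the previous window's loss and totals 20%. The four strengths are odds ratios of about 1, 1.4, 1.9 and 7 per SD of month-3 loss.

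| Dropout on poor earlier loss | Mean, weighed | Mean, missing | Mean, model on all weights | 5% rate, weighed | 5% rate, missing as non-response |
|---|---|---|---|---|---|
| None | 4.80 | 4.81 | 4.80 | 48% | 38% |
| Weak | 4.99 | 4.07 | 4.80 | 50% | 40% |
| Modest | 5.17 | 3.36 | 4.81 | 52% | 41% |
| Strong | 5.68 | 1.32 | 4.79 | 56% | 45% |

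The bias in the mean equals the missing fraction times the gap between weighed and missing women. For modest dropout it is 0.2 × (5.17 − 3.36) = 0.36, and for strong dropout 0.2 × (5.68 − 1.32) = 0.87. If the women who lose more are the ones who stop, the weighed-only mean is instead 4.44 (modest) or 3.94 (strong), and the model still gives about 4.80. Imputing the 5% rate from the model gives 48% in all four rows.

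**Step 4. How much of the gain survives at n = 30.** Root-mean-square error of the mean with regular weighing, weighed-only against model:

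- Random dropout: 0.87 against 0.81.
- Modest dropout: 0.92 against 0.81.
- Strong dropout: 1.18 against 0.81.
- No missing data, for reference: 0.77.

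**Step 5. Where the model does less well.**

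- If each interim window is sent with probability 0.6 or 0.3, the model mean under strong dropout is 5.00 or 5.27, against 5.67 weighed-only. It removes 0.67/0.87 = 77% or 0.40/0.87 = 46% of the bias.
- If strong dropout depends on loss not yet transmitted, the model leaves 5.13 against 5.90.

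**The case against.** The strongest reply is that this is a small descriptive pilot. The protocol says "this trial is not meant to be adequately powered for testing hypothesized effects" and promises counts and reasons for missed follow-up, so with raw counts a reader can compute either denominator and both bounds. No go/no-go rule or sample size is said to rest on this mean. Except under strong dropout, the gain in step 4 is 0.06 to 0.11 percentage points against a sampling SE of 0.76. The simulation also uses data that suit the model. All of this stands, and it is why the point is minor. Counts do not, however, let a reader adjust the mean.

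A second reply is that the plan never specifies a weighed-only analysis, and that the coaching sentence does not exclude other uses of the weights. This is also fair. A reader might infer that the protocol chose a completer analysis, but it is silent. Leaving these women out follows only because no other method is given. The missing window likewise holds for the readable text only, since a figure after the assessment steps is not shown.

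A third reply is that the shifts in step 2 from weighed-only to missing-as-non-response (about 6, 12 and 19 points) overstate the problem. Read as bias, they do. In step 3, counting missing women as non-responders lies further from the true 48% than the weighed-only rate in three of the four rows.

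**Conclusion.** The point holds as a minor improvement to the analysis. As written, the primary mean omits women without a month-4 weight, and the 5% rate may do the same, while usable earlier weights are given no role in the analysis.

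With 20% missing and an SD of about 4.15, the weighed-only bias is about 0.2 to 0.4 percentage points in the mean and 2 to 4 points in the 5% rate for weak to modest dropout. For strong dropout it is about 0.9 and 8. Only in the strong case does the bias in the mean exceed the sampling SE of about 0.76. With random dropout it is zero.

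A reader might infer that the pilot will overstate weight loss. The documents do not support a direction: if the women who do well stop weighing, the loss is understated. Nor do they support calling the study invalid, since it tests no hypothesis and claims no power. The undefined window and denominator are, on their own, missing detail.

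**What to change.** In section 4.0:

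1. Estimate the mean percent change and the 5% rate at month 4 for all enrolled women from all transmitted scale weights. Use either a repeated-measures model with time in categories (for example monthly windows) and a simple covariance, or multiple imputation of the month-4 weight from earlier weights. Avoid a straight line in time, because section 3.0 allows about a month for the diet to change fully.
2. Report the planned weighed-only mean, SD and rate alongside. For the 5% rate, add the missing-as-non-response and missing-as-response bounds as sensitivity results.
3. Take the month-4 weight from scale readings in a stated window around week 16, for example the mean over 7 days.
4. State the missing-at-random assumption, and report how many women without a month-4 weight had earlier readings.

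The cost is a few lines of text and a little more analysis of data the scale already sends, with no added visit or procedure. The downside is reliance on missing at random. The gain is small if dropout is low or random, or if women stop weighing early.

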## Intervention outcomes at 4 months

### Intervention feasibility and acceptability

Other measures	PCOS-related quality of life [40], general quality of life (from Patient-Reported Outcomes Measurement Information System or PROMIS, which includes depressive symptoms, energy levels, pain, and sleep quality)[41], physical activity [42, 43], dietary adherence (macronutrient levels assessed with a 3-day food record), food cravings [44], stress eating [45, 46], dietary-based social support [47].
----------------	--

